### 5.2.4 Duration / Study Day / Time

Study day will be calculated as the number of days from first dose of study drug.

- For events on or after the first dose, then
  - study day = date of event – date of first dose of study drug + 1
- For events before the first dose, then
  - study day = date of event – date of first dose of study drug

### 5.2.5 Conventions for Missing and Partial Dates

It is not expected that there will be any missing dates for events occurring during study conduct. Historical dates such as dates of medical history or prior medications may be missing or partial. Dates (historical or during study conduct) will only be imputed if a full date is needed for a calculation or to support a definition.

All dates presented in the individual participant listings will be as recorded on the Electronic Case Report Form (eCRF).

#### 5.2.5.1 Missing Adverse Events Dates

In the rare case that an AE start date or time is missing and it is unclear whether the AE is treatment emergent or not then a conservative approach will be taken, and it will be assumed that the AE is treatment emergent and occurred after first dosing. If an adverse event stop date is missing it will be assumed that the AE is ongoing.

QMD Ref: Worldwide-TMP-ST-054-1.0_Effective: 12Aug2022	Governing QMD: Worldwide-SOP-ST-026
Confidentiality Statement	
This document is the property of Worldwide Clinical Trials Inc. and may not be duplicated, copied, altered or removed from company without prior approval from Worldwide Quality Assurance or in compliance with Worldwide Standard Operating Procedures.	

Worldwide Clinical Trials Controlled Quality Management Document		
 WORLDWIDE CLINICAL TRIALS	Sponsor:	Eli Lilly and Company
	Protocol Number:	J4N-MC-YFAA
STATISTICAL ANALYSIS PLAN		

## 5.2.6 Inexact Values

In the case where a variable is recorded as “> x”, “≥ x”, “< x” or “≤ x”, a value of x will be taken for analysis purposes.

See section 5.9.2 for methods for handling inexact values specifically for PK concentration data.

## 5.2.7 Electrocardiogram (ECG) Data

For ECG data recorded on continuous scales, if replicate (i.e., triplicate) values are recorded at a time point, the mean or the replicates rounded to the integer will be used for summarization. For overall interpretation if more than one value is recorded, the most severe (worst case) of the respective readings will be taken.

## 5.2.8 Unscheduled Visits

Only scheduled post-baseline laboratory and vital signs values will be tabulated unless otherwise stated. Post-baseline repeat / unscheduled assessments will be included in all listings in the relevant appendices to the CSR.

## 5.2.9 Pharmacokinetic Parameters

### 5.2.9.1 Plasma PK Parameters

The following PK parameters in plasma will be calculated for LY3885125 for single dose cohorts (Part A):

Parameter	Definition
$C_{\max}$	Maximum observed concentration
$T_{\max}$	Time of the maximum concentration
$AUC_{0-24}$	Area under the concentration-time curve from time-zero 24 h postdose; calculated using the linear trapezoidal rule
$AUC_{\text{last}}$	Area under the concentration-time curve from time-zero to the time of the last quantifiable concentration; calculated using the linear trapezoidal rule
$AUC_{\text{inf}}$	Area under the concentration-time curve from time-zero extrapolated to infinity; calculated as:  $AUC_{\text{inf}} = AUC_{\text{last}} + C_{\text{last}}/\lambda_z$ Note: Additional criteria for reporting $AUC_{\text{inf}}$ are summarized below

QMD Ref: Worldwide-TMP-ST-054-1.0_Effective: 12Aug2022	Governing QMD: Worldwide-SOP-ST-026
Confidentiality Statement	
This document is the property of Worldwide Clinical Trials Inc. and may not be duplicated, copied, altered or removed from company without prior approval from Worldwide Quality Assurance or in compliance with Worldwide Standard Operating Procedures.	

Worldwide Clinical Trials Controlled Quality Management Document		
 WORLDWIDE CLINICAL TRIALS	Sponsor:	Eli Lilly and Company
	Protocol Number:	J4N-MC-YFAA
STATISTICAL ANALYSIS PLAN		

Parameter	Definition
$AUC_{\text{Extrap}} (\%)$	Percentage of $AUC_{\text{inf}}$ based on extrapolation; calculated as: $AUC_{\text{Extrap}} = 100 \times [1 - (AUC_{\text{last}}/AUC_{\text{inf}})]$
$\lambda_z$ (Lambda-z, $k_{\text{el}}$ )	Apparent elimination rate constant; calculated as the slope of the linear regression through the terminal log-linear segment of the concentration-time curve Note: Additional criteria for reporting $\lambda_z$ are summarized below
$t_{1/2}$	Observed terminal elimination half-life; calculated as: $t_{1/2} = \ln(2)/\lambda_z$
$CL/F$	Apparent total body clearance after SC administration, calculated as: $CL/F = \text{Dose}/AUC_{\text{inf}}$ , where F is the bioavailability
$V_z/F$	Apparent volume of distribution after SC administration, calculated as: $V_z/F = \text{Dose}/(AUC_{\text{inf}} \times \lambda_z)$ , where F is the bioavailability
$C_{\text{last}}$	Last observed quantifiable concentration
$T_{\text{last}}$	Time of the last observed quantifiable concentration

#### Lambda-z ( $\lambda_z$ ) and $AUC_{\text{inf}}$ Reporting Criteria

The following criteria will be used to report  $\lambda_z$ :

- At least three quantifiable concentrations will be used in the regression
- $C_{\text{max}}$  or data prior to  $C_{\text{max}}$  will not be included in the regression.
- The adjusted regression coefficient ( $R^2$  adj) should be  $\geq 0.80$ .

If these acceptance criteria are not met,  $\lambda_z$  reported for individual subjects will be retained in PK parameter tables for informational purposes;  $\lambda_z$  will be excluded from summary statistics. Parameters calculated using  $\lambda_z$  ( $t_{1/2}$ ,  $CL/F$ ,  $V_z/F$ ) will be reported as ND (not determinable). Lambda-z ( $\lambda_z$ ) and descriptive parameters ( $\lambda_z$  time range, Adj  $R^2$ , etc.) will be presented in a separate listing.

If lambda-z acceptance criteria are met and  $AUC_{\text{inf}}$  is estimable, the following criteria are used to report  $AUC_{\text{inf}}$ :

QMD Ref: Worldwide-TMP-ST-054-1.0_Effective: 12Aug2022	Governing QMD: Worldwide-SOP-ST-026
Confidentiality Statement	
This document is the property of Worldwide Clinical Trials Inc. and may not be duplicated, copied, altered or removed from company without prior approval from Worldwide Quality Assurance or in compliance with Worldwide Standard Operating Procedures.	

Worldwide Clinical Trials Controlled Quality Management Document		
 WORLDWIDE CLINICAL TRIALS	Sponsor:	Eli Lilly and Company
	Protocol Number:	J4N-MC-YFAA
STATISTICAL ANALYSIS PLAN		

- The percentage of AUCinf based on extrapolation should be <20.0%.

If the percentage of AUCinf based on extrapolation is 30.0% or greater, AUCinf and AUCExtrap will be retained in a PK parameter table for informational purposes; these parameters will be excluded from summary statistics, subsequent PK calculations (e.g., CL/F and Vz/F), and statistical analysis (e.g., ANOVA).

### 5.2.9.2 Urine PK Parameters

The following PK parameters in urine will be calculated for LY3885125 after single doses (Part A):

Parameter	Definition
Ae	Amount of drug excreted in urine for each collection interval, calculated as: $Ae = \text{concentration} \times \text{volume}$
Total Ae	Total amount of drug excreted over the entire 24-hour sampling interval
Fe (%)	Percentage of dose excreted in urine for each collection interval, calculated as: $Fe (\%) = Ae / \text{Dose} \times 100$
Total Fe (%)	Total percentage of dose excreted in urine over the entire 24-hour sampling interval, calculated as: $\text{Total Fe} (\%) = \text{Total Ae} / \text{Dose} \times 100$
CL r	Renal clearance, calculated as: $CL_r = \text{Total Ae} / AUC_{0-24}$

### 5.2.10 Classification of ADA

Subjects are classified according to the following table for ADA.

ADA category	Criteria
Subjects with baseline immunogenicity data	Subjects with a valid ADA assessment at baseline
Subjects with post-baseline immunogenicity data	Subjects with any valid ADA assessment post-baseline

QMD Ref: Worldwide-TMP-ST-054-1.0_Effective: 12Aug2022	Governing QMD: Worldwide-SOP-ST-026
Confidentiality Statement This document is the property of Worldwide Clinical Trials Inc. and may not be duplicated, copied, altered or removed from company without prior approval from Worldwide Quality Assurance or in compliance with Worldwide Standard Operating Procedures.	

Worldwide Clinical Trials Controlled Quality Management Document		
 WORLDWIDE CLINICAL TRIALS	Sponsor:	Eli Lilly and Company
	Protocol Number:	J4N-MC-YFAA
STATISTICAL ANALYSIS PLAN		

ADA category	Criteria
Subjects with baseline and post-baseline immunogenicity data	Subjects with both a valid ADA assessment at baseline and any valid ADA assessment post-baseline
Subjects with baseline or post-baseline immunogenicity data	Subjects with any valid ADA assessment at baseline or post-baseline
ADA+ prevalence at baseline	Subjects with a positive ADA assessment at baseline
ADA+ prevalence at post-baseline	Subjects with any positive ADA assessment post-baseline
ADA+ prevalence at both baseline and post-baseline	Subjects with both a positive ADA assessment at baseline and any positive ADA assessment post-baseline
ADA Positive at baseline or post-baseline	Subjects with any positive ADA assessment at baseline or post-baseline
Treatment-Emergent ADA+	Treatment-boosted ADA+; or treatment-induced ADA+
Treatment-boosted ADA+	Subjects who were ADA positive at both baseline and post-baseline, but had an increase in ADA titer from baseline to post-baseline
Treatment-induced ADA+	Subjects who were ADA negative or missing at baseline and became ADA positive post-baseline

ADA prevalence is defined as the proportion of subjects in category “ADA Positive”.

ADA incidence is defined as the proportion of subjects in category “Treatment-Emergent ADA+”.

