#### 5.1.6 Immunogenicity Analysis Set

All participants who are exposed to study intervention and who had at least one valid (non-missing and interpretable) baseline or post-baseline immunogenicity assessment.

The Immunogenicity analysis set is used for the Immunogenicity analyses.

QMD Ref: Worldwide-TMP-ST-054-1.0_Effective: 12Aug2022	Governing QMD: Worldwide-SOP-ST-026
Confidentiality Statement This document is the property of Worldwide Clinical Trials Inc. and may not be duplicated, copied, altered or removed from company without prior approval from Worldwide Quality Assurance or in compliance with Worldwide Standard Operating Procedures.	

Worldwide Clinical Trials Controlled Quality Management Document		
 WORLDWIDE CLINICAL TRIALS	Sponsor:	Eli Lilly and Company
	Protocol Number:	J4N-MC-YFAA
STATISTICAL ANALYSIS PLAN		

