### 5.3 Conventions

All data listings, summaries, figures, and statistical analyses will be generated using SAS version 9.4 or higher.

Part A summaries will be presented by treatment group. Treatment group labels for Part A TFLs will be displayed as follows, with the addition of “Part A Overall (N=XX)”, when appropriate:

QMD Ref: Worldwide-TMP-ST-054-1.0_Effective: 12Aug2022	Governing QMD: Worldwide-SOP-ST-026
Confidentiality Statement This document is the property of Worldwide Clinical Trials Inc. and may not be duplicated, copied, altered or removed from company without prior approval from Worldwide Quality Assurance or in compliance with Worldwide Standard Operating Procedures.	

Worldwide Clinical Trials Controlled Quality Management Document		
 WORLDWIDE CLINICAL TRIALS	Sponsor:	Eli Lilly and Company
	Protocol Number:	J4N-MC-YFAA
STATISTICAL ANALYSIS PLAN		

LY3885125 CCI (N=XX)	LY3885125 CCI (N=XX)	LY3885125 CCI (N=XX)	LY3885125 CCI (N=XX)	LY3885125 CCI (N=XX)	Pooled LY3885125 (N=XX)	Pooled Placebo (N=XX)
-----------------------------------	-----------------------------------	-----------------------------------	-----------------------------------	-----------------------------------	-------------------------------	-----------------------------

Part A listings will be sorted in the following order: treatment group, participant, parameter, and visit unless otherwise stated. All data will be listed, participants who were not randomized will be displayed after the randomized treatment groups/ arms.

Continuous variables will be summarized by the number of non-missing observations, mean, median, standard deviation, and minimum and maximum.

Categorical variables will be summarized by presenting the frequency and percent. Percentages will be based on the number of participants in the column header unless otherwise specified in the footnote. For each variable, all categories will be shown. Zero frequencies (but not the percent) within a category will be presented.

Means, medians and percentiles will be displayed to one more decimal place than the data, dispersion statistics (e.g., standard deviation) will have two more decimal places, and the minimum and maximum will be displayed to the same number of decimal places as reported in the raw data. Percentages will be displayed with one decimal place.

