### 5.12 Immunogenicity Analysis

The n count and % for each immunogenicity parameter will be summarized for all subjects in the Immunogenicity Analysis Set by treatment group.

Worldwide Clinical Trials Controlled Quality Management Document		
 WORLDWIDE CLINICAL TRIALS	Sponsor:	Eli Lilly and Company
	Protocol Number:	J4N-MC-YFAA
STATISTICAL ANALYSIS PLAN		

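### ADA incidence: any titre rise counts as treatment-boosted, and baseline-only participants fall in the default denominator, so the exploratory rate can be biased in either direction

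*SAP*

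**What the plan says.** SAP 5.2.10 builds treatment-emergent ADA from two categories:

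- **Treatment-boosted:** positive at baseline and post-baseline, "but had an increase in ADA titer from baseline to post-baseline". No fold change, number of dilution steps or assay-based margin is given. Where there are several post-baseline samples, the text does not say which one is compared.
- **Treatment-induced:** "Subjects who were ADA negative or missing at baseline and became ADA positive post-baseline".

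The rate is then introduced with "ADA incidence is defined as the proportion of subjects in category", followed by the treatment-emergent category. The definition names no denominator.

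Three other places supply one by default:

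- SAP 5.1.6 admits exposed participants "who had at least one valid (non-missing and interpretable) baseline or post-baseline immunogenicity assessment", so a baseline sample alone is enough.
- SAP 5.12 says the count and percentage for each immunogenicity parameter "will be summarized for all subjects in the Immunogenicity Analysis Set by treatment group".
- SAP 5.3 adds: "Percentages will be based on the number of participants in the column header unless otherwise specified in the footnote".

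SAP 5.2.10 also defines categories for participants with valid post-baseline data and for those with valid data both at baseline and afterwards, but does not tie either to the incidence calculation. SAP Section 2 lists immunogenicity as exploratory. Protocol 8.9 says that a validated assay is used and that titres of confirmed positives are reported.

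**The concern.** A titre is read from serial dilutions, and repeat readings of an unchanged sample can differ. If any rise counts, some baseline-positive participants will be called treatment-boosted although nothing changed. The chance grows if the highest of several post-baseline titres is the one compared. Placebo participants are tested under the same rule and can be given the same label.

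A participant with no post-baseline result cannot enter the numerator. Keeping that person in the denominator treats an unknown outcome as a negative one.

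At stake is how the ADA table is read across dose groups in a first-in-human oligonucleotide study. With so few participants per dose, one or two classifications could suggest a dose trend or hide one. Because the two rules push in opposite directions, a reader of the percentage alone cannot tell which way it is off.

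**Working it through.** **1. Group sizes.** The cohort sizes are redacted, but Protocol 4.1.1 gives allocation ratios of 6:2 (Cohorts 1-2), 9:2 (Cohorts 3-5) and 10:9 (Cohort 6). Read as counts:

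2 × (6+2) + 3 × (9+2) + (10+9) = 16 + 33 + 19 = 68.

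This reproduces the approximately 68 Part A completers in Protocol 9.5. Cohort 6 was not enrolled (SAP Section 3), which leaves 68 − 19 = 49:

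- active: 2 × 6 + 3 × 9 = 39, in dose groups of 6, 6, 9, 9 and 9;
- pooled placebo: 5 × 2 = 10.

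The SAP Section 4 table shows 30 for Cohorts 1 and 2 in the text available. That fits neither the 6:2 ratio nor the total of 68, so it is treated as a redaction or text-reading artefact and not used.

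**2. One participant reclassified in the numerator** moves the rate by 100/N points:

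| Group | N | Points |
|---|---|---|
| Cohort 1 or 2, active | 6 | 16.7 |
| Cohort 3, 4 or 5, active | 9 | 11.1 |
| Pooled placebo | 10 | 10.0 |
| Pooled active | 39 | 2.6 |

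**3. Titre rule.** The documents give no dilution scheme, titre precision or number of samples, so these are assumptions. Let there be no true change, and let each reading, baseline included, fall one step up with probability p, one step down with probability p, and otherwise be unchanged. Compare the highest of k post-baseline readings with baseline:

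- P(any rise) = 1 − [p·p^k + (1−2p)(1−p)^k + p]
- P(rise of at least two steps) = p·[1 − (1−p)^k]

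| p | k | Any rise | At least two steps |
|---|---|---|---|
| 0.10 | 1 | 17.0% | 1.0% |
| 0.25 | 1 | 31.3% | 6.3% |
| 0.10 | 3 | 31.7% | 2.7% |
| 0.25 | 5 | 63.1% | 19.1% |

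A second noise model was simulated: normal reading error with SD 0.3 to 0.7 log2 on a two-fold grid, and 1 to 4 post-baseline samples. It gave 17% to 59% for any rise and 0.1% to 19% for at least two steps.

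These are shares of **baseline-positive** participants, not of the group. The expected addition to incidence is the baseline-positive rate q times the share. No q is given. For an assumed q of 2% to 10%, the addition runs from 0.02 × 17.0% = 0.3 points to 0.10 × 63.1% = 6.3 points. Put another way, each baseline-positive participant in the pooled active column adds between 0.170/39 = 0.4 and 0.631/39 = 1.6 points on average.

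**4. Denominator.** With x treatment-emergent cases among N, one of whom has only a baseline sample, the rate changes from x/N to x/(N−1). The difference is x/[N(N−1)], which cannot exceed 1/N because x is at most N−1. With assumed counts:

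- 2/6 = 33.3% becomes 2/5 = 40.0%
- 3/9 = 33.3% becomes 3/8 = 37.5%
- 8/39 = 20.5% becomes 8/38 = 21.1%

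SAP 5.2.3 excludes early termination assessments from tabulations. If that covers ADA, a participant whose only post-baseline sample was taken at early termination also becomes baseline-only.

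**5. Missing baseline.** Taking one missing-baseline positive out of numerator and denominator changes 1/9 = 11.1% to 0/8 = 0%, and 4/39 = 10.3% to 3/38 = 7.9%.

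**The case against.** The case for leaving the text alone has real substance.

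- **The endpoint is modest.** SAP Section 2 words it as prevalence of immunogenicity statuses and lists it as exploratory. Incidence is a derived term in 5.2.10, and no stated decision rule uses it. This stands and limits the importance of the point.
- **The error may be nil.** A reader might infer that the reported incidence is bound to be wrong. The documents do not support that. With no small titre rises and no participants lacking post-baseline samples, the boosted and denominator rules distort nothing.
- **The noise figures are assumed.** A reader might take 32% to 63% as the inflation of incidence. Those figures apply only to baseline-positive participants and compare the maximum of 3 to 5 visits, which the SAP does not specify. With a single compared sample they fall to 17% to 31%. The gap between an any-rise rule and a two-step rule remains in every setting tried.
- **No fixed fold threshold follows from the documents.** They state no dilution scheme, so a mandatory four-fold rule cannot be supported from them. A margin tied to the validated assay can.
- **Counting missing-baseline positives as induced is defensible.** It may look like an error, but it matches the SAP's conservative handling elsewhere: adverse events of unclear timing are treated as treatment-emergent (5.2.5.1), and missing causality and severity are set to the worse category (5.11.1). It supports only separate display.
- **The denominator could be set in a footnote.** SAP 5.3 allows this and the table shells are not in the documents. Also, the rows 5.2.10 defines would let a reader recompute the rate. But no SAP text overrides the default, and an unseen footnote cannot be assumed.

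**Conclusion.** The point holds as a weakness in two stated rules. Followed as written, SAP 5.2.10 counts a titre rise within assay variability as treatment-emergent, which can only raise incidence. SAP 5.1.6, 5.12 and 5.3 together place baseline-only participants in the default denominator, which can only lower it. The net direction is not fixed.

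The practical size is the weight of one participant per dose column: 11.1 or 16.7 points for a numerator change, and no more than that for a denominator change. In the pooled active column it is 2.6 points. This rests on reading the allocation ratios as counts, which the total of 68 supports. How often such participants will occur cannot be judged from the documents. The primary safety analysis is unaffected. The change is worth making because the rate will be read by dose and the repair is small.

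**What to change.** 1. **SAP 5.2.10, treatment-boosted.** Require a post-baseline titre that exceeds baseline by more than the validated assay variability; two dilution steps would serve as an example if the assay's dilution scheme supports it. State which post-baseline sample is compared, for instance the highest or the last.
2. **SAP 5.12, denominator.** Name the category already defined in 5.2.10, participants with a valid result at baseline and at least one afterwards, as the denominator for treatment-emergent incidence, and repeat this in a footnote to Table 14.3.4.10. State whether early termination samples count towards classification.
3. **Missing-baseline positives.** Show them on their own row and leave them out of the main numerator, so that incidence can be read with and without them. The version that includes them can use the existing category of participants with any valid post-baseline result.

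The cost is a few sentences of SAP text and reprogramming one table. A few participants leave the main rate, which makes small denominators slightly smaller. SAP Section 5 requires approval before Part A database lock; after lock the change would go into the post-lock addendum.

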### 5.3 Conventions

All data listings, summaries, figures, and statistical analyses will be generated using SAS version 9.4 or higher.

Part A summaries will be presented by treatment group. Treatment group labels for Part A TFLs will be displayed as follows, with the addition of “Part A Overall (N=XX)”, when appropriate:

QMD Ref: Worldwide-TMP-ST-054-1.0_Effective: 12Aug2022	Governing QMD: Worldwide-SOP-ST-026
Confidentiality Statement This document is the property of Worldwide Clinical Trials Inc. and may not be duplicated, copied, altered or removed from company without prior approval from Worldwide Quality Assurance or in compliance with Worldwide Standard Operating Procedures.	

Worldwide Clinical Trials Controlled Quality Management Document		
 WORLDWIDE CLINICAL TRIALS	Sponsor:	Eli Lilly and Company
	Protocol Number:	J4N-MC-YFAA
STATISTICAL ANALYSIS PLAN		

LY3885125 CCI (N=XX)	LY3885125 CCI (N=XX)	LY3885125 CCI (N=XX)	LY3885125 CCI (N=XX)	LY3885125 CCI (N=XX)	Pooled LY3885125 (N=XX)	Pooled Placebo (N=XX)
-----------------------------------	-----------------------------------	-----------------------------------	-----------------------------------	-----------------------------------	-------------------------------	-----------------------------

Part A listings will be sorted in the following order: treatment group, participant, parameter, and visit unless otherwise stated. All data will be listed, participants who were not randomized will be displayed after the randomized treatment groups/ arms.

Continuous variables will be summarized by the number of non-missing observations, mean, median, standard deviation, and minimum and maximum.

Categorical variables will be summarized by presenting the frequency and percent. Percentages will be based on the number of participants in the column header unless otherwise specified in the footnote. For each variable, all categories will be shown. Zero frequencies (but not the percent) within a category will be presented.

Means, medians and percentiles will be displayed to one more decimal place than the data, dispersion statistics (e.g., standard deviation) will have two more decimal places, and the minimum and maximum will be displayed to the same number of decimal places as reported in the raw data. Percentages will be displayed with one decimal place.

PK data listings, summaries, figures, and statistical analyses will be generated using Phoenix™ WinNonlin® (Version 8.3.4.295 or higher) or SAS (Version 9.4 or higher). PK concentration data will be summarized by treatment/dose level at each nominal sample time. PK parameter data will be summarized by treatment/dose level.

Plasma PK concentration-time data and PK parameters will be summarized by the number of non-missing observations (n), mean, standard deviation (SD), median, minimum (min), maximum (max), coefficient of variation (CV%), geometric mean (geo. mean), and geometric mean CV%.

Urine PK concentrations, Ae, and Fe% will be summarized by n, mean, SD, median, min, max, and CV% for each collection interval. Urine PK parameters (Total Ae, Total Fe%), CLr) will be summarized by n, mean, SD, median, min, max, CV%, geo. mean, and geo. CV%.

Individual subject plasma PK data (concentration-time data and PK parameters) will be reported to 3 significant figures. For summary statistics, n will be reported as a whole number; mean, standard deviation, median, minimum, maximum, CV%, geometric mean, and geometric mean CV% will be reported to 3 significant figures. For the dose proportionality assessment, slope will be presented to 4 decimal places and associated 90% confidence intervals will be reported to 2 decimal places.

QMD Ref: Worldwide-TMP-ST-054-1.0_Effective: 12Aug2022	Governing QMD: Worldwide-SOP-ST-026
Confidentiality Statement This document is the property of Worldwide Clinical Trials Inc. and may not be duplicated, copied, altered or removed from company without prior approval from Worldwide Quality Assurance or in compliance with Worldwide Standard Operating Procedures.	

Worldwide Clinical Trials Controlled Quality Management Document		
 WORLDWIDE CLINICAL TRIALS	Sponsor:	Eli Lilly and Company
	Protocol Number:	J4N-MC-YFAA
STATISTICAL ANALYSIS PLAN		

